8.5.2 Paternal exposure

Male patients should refrain from fathering a child or donating sperm during the study and for 180 days after the last dose of Nirogacestat.

Pregnancy of the patient's partner is not considered to be an AE. However, the outcome of all pregnancies (spontaneous miscarriage, elective termination, ectopic pregnancy, normal birth, or congenital abnormality) occurring from the date of the first dose until 30 days after the last dose should, if possible, be followed up and documented.

8.6 REGULATORY REPORTING FOR STUDIES CONDUCTED UNDER CCR-SPONSORED IND

Following notification from the investigator, CCR, the IND sponsor, will report any suspected adverse reaction that is both serious and unexpected. CCR will report an AE as a suspected adverse reaction only if there is evidence to suggest a causal relationship between the study product and the adverse event. CCR will notify FDA and all participating investigators (i.e., all investigators to whom the sponsor is providing drug under its INDs or under any investigator's IND) in an IND safety report of potential serious risks from clinical trials or any other source, as soon as possible, in accordance to 21 CFR Part 312.32.

All serious events will be reported to the FDA at least annually in a summary format.

Version Date: 5-18-2023

9 CLINICAL MONITORING

As a sponsor for clinical trials, FDA regulations require the CCR to maintain a monitoring program. The CCR's program allows for confirmation of: study data, specifically data that could affect the interpretation of primary and secondary study endpoints; adherence to the protocol, regulations, ICH E6, and SOPs; and human subjects protection. This is done through independent verification of study data with source documentation focusing on:

- Informed consent process
- Eligibility confirmation
- Drug administration and accountability
- Adverse events monitoring
- Response assessment.

This trial will be monitored by personnel employed by a CCR contractor. Monitors are qualified by training and experience to monitor the progress of clinical trials. Personnel monitoring this study will not be affiliated in any way with the trial conduct.

10 STATISTICAL SECTION

This study will be conducted as a single stage Phase II trial to rule out an unacceptably low 10% clinical response rate (PR+CR; p0=0.10) in favor of a modestly high response rate of 35% (p1=0.35). If we assume a type I error rate (alpha, probability of accepting a poor treatment) of 0.10 when the response rate is 0.10 and a statistical power of 0.90 (beta=0.10, probability of rejecting a good treatment) when the true response rate is 0.35, then we plan to accrue a total of 17 patients. The null hypothesis will be rejected if 4 or more responses are observed in the 17 patients. It is anticipated that 1 patient per month may be enrolled onto this study. Thus, it will take approximately 17 months to complete enrollment.

10.1 STATISTICAL CONSIDERATIONS FOR EXPLORATORY CORRELATIVE STUDIES

Symptom measurements will be summarized by mean and standard deviation for continuous measurements and by frequency distributions for categorical measurements. Mutations in *APC* and *CTNNB1* will be summarized with frequency distributions, respectively. The clinical response rate will be compared between the mutated and non-mutated subgroups. Modulation of the Notch pathway will be assessed by a paired t-test for a change in expression from baseline to post-drug administration.

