3 STUDY IMPLEMENTATION

3.1 STUDY DESIGN

This is an open-label Phase II trial of Nirogacestat. Study drug will be administered at 150 mg, orally, BID, continually, in 21-day cycles.

Labs (CBC with differential and serum chemistries, including electrolytes) will be monitored each week during cycle 1, and then every other cycle. History and physical examination will be performed before the start of every other cycle. For patients having a history and physical examination performed by their local physician, study drug will be held until receipt of results; this may result in an interruption of therapy. For patients on study for more than a year, history and physical examination and labs can be performed every 3 cycles (up to 2 weeks before the start of the cycle). EKG monitoring will be performed at baseline and then post-drug administration on study day 1. Additional EKG monitoring may be performed during cycle 1 as clinically indicated.

Response assessment will be performed using RECIST 1.1. Restaging scans (CT scans of the known site of disease) will be performed at baseline prior to starting study treatment and then every 6 cycles (+/- 1 cycle) as described in Section 5.5. An MRI with diffusion weighting may be performed prior to start of study treatment, end of cycle 1, and at the time of restaging, per PI's discretion.

Health-related quality of life (HRQOL)/symptom questionnaires will be administered at baseline and at restaging (response assessment) as described in Section 3.4.

Archival unstained slides or tumor block will be sent for genetic research studies as described in Section 5.4.

Blood for research (whole exome sequencing) will be collected at baseline as described in Section 5.2.

Optional tumor biopsies for research purposes will be performed at baseline prior to study treatment and at the beginning of cycle 7 (+/- one cycle) as described in Section 5.2.

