3.4 PATIENT REPORTED OUTCOME QUESTIONNAIRE

Participants on this study will be asked to complete health-related quality-of-life (HRQOL)/symptom questionnaires to assess the severity and associated interference caused by disease and treatment-related symptoms and track their severity and interference over the course of treatment. These patient-reported outcome (PRO) measures will capture the emergence or worsening of selected symptoms from baseline to study completion, thus improving the identification of treatment-emergent symptomatic toxicity and better capturing improvements in disease-related symptoms which may inform decisions about therapeutic response and clinical benefit Such patient-reported outcomes (PRO) allow participants to rate their own HRQOL, thereby providing a direct measure of each patient's experience of treatment over the course of the study [26, 27].

This protocol will use the psychometrically-validated M.D. Anderson Symptom Inventory (MDASI) to assess PRO disease and treatment-related symptoms [28]. MDASI uses a 0-10 numerical scale to assess, over the previous 24 hours, 13 symptoms commonly experienced by patients with cancer and 6 additional items that assess the extent to which these symptoms interfered with how patients felt and were able to function:

- 13 treatment symptoms assessed: pain, fatigue, nausea, disturbed sleep, distress (emotional), shortness of breath, lack of appetite, drowsiness, dry mouth, sadness, vomiting, difficulty remembering, and numbness or tingling
- 6 symptom interference items assessed: general activity, mood, walking ability, normal work, relations with other people, and enjoyment of life

A copy of MDASI is provided in Appendix D. The questionnaires will be administered at baseline and at restaging. Completing the MDASI takes approximately 2-5 minutes and the symptom scale will take an additional 5 minutes to complete. All patients will complete these questionnaires under the supervision of a member of the clinic staff.

A component score representing symptom severity is obtained by taking the average of the 13 symptom items together. A component score representing symptom distress is obtaining by averaging the 6 symptom interference items. Questionnaires will be maintained in the research chart of each patient. The NCI has received permission to use MDASI by the copyright holder, The University of Texas MD Anderson Cancer Center.

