3.5 STUDY CALENDAR

Baseline history and physical exam are to be conducted within 1 week prior to start of protocol therapy; laboratory evaluations must be done within 72 hours prior to start of protocol therapy. Scans and x-rays must be done ≤ 28 days prior to the start of therapy. The duration of a cycle will be 21 days (\pm 1 day for scheduling). The start of the next cycle may be delayed for up to 1 week to accommodate scheduling conflicts. History and physical examination and laboratory

Version Date: 5-18-2023

evaluations can be performed before the start of a cycle. For patients having their history and physical examination performed by their local physician, study drug will be held until receipt of results. For patients on study for more than a year, history, physical examination, and labs can be performed every 3 cycles (up to 2 weeks before the start of the cycle).

Version Date: 5-18-2023

	Pre- Study	C1 W1 (D1-7)	C1 W2 (D8-14)	C1 W3 D15-21)	C2 W1 (D1-7)	C2 W2 (D8-14)	C2 W3 (D15-21)	C3 W1 on	Off Treat- ment
Nirogacestat (PF- 03084014) ^a		X	X	X	X	X	X	X	
Informed consent	X								
Demographics	X								
Medical history	X								
Concurrent meds	X	X						X	
Physical exam ^b	X							X	X
Vital signs ^b	X							X	X
Height	X								
Weight b	X							X	X
Performance status ^b	X							X	X
CBC w/diff, plts ^c	X		X	X				X	X
Serum chemistry ^c	X		X	X				X	X
Coagulation profile	X								
Adverse event evaluation		X						X	X
Tumor measurements d	X								X
B-HCG ^e	X								
EKG ^f	X								
Tumor biopsies g	X								
Archival tissue h									
PG blood sampling h	X								
Questionnaire i	X								

- a. PF-03084014 twice daily in 21-day cycles.
- b. Should be performed on day 1 at the Clinical Center, and then at the start of every other cycle at the Clinical Center or by patient's local physician. For patients on study more than a year, history and physical examination can be performed every 3 cycles (up to 2 weeks before the start of the cycle).
- c. Serum chemistry (albumin, alkaline phosphatase, total bilirubin, BUN, calcium, creatinine, glucose, phosphorus, magnesium, potassium, SGOT [AST], SGPT [ALT], sodium) and CBC w/diff, platelets should be performed within 72 hours before enrollment (pre-study) and weekly during cycle 1, at the start of every other cycle and as clinically indicated. For patients on study more than a year, labs can be performed every 3 cycles (up to 2 weeks before the start of the cycle).

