- d. Tumor measurements are repeated every 6 cycles (±1 cycle). Documentation (radiologic) must be provided for patients removed from study for progressive disease. Optional MRI scans may be performed prior to start of study treatment, end of cycle 1, and every 6 cycles.
- e. Serum or urine pregnancy test (women of childbearing potential) within 1 week prior to enrollment

- f. EKG at baseline and then post-drug administration on day 1. Additional monitoring may be performed during cycle 1 as clinically indicated.
- g. Tumor biopsies are optional at baseline and at the beginning of cycle 7
- h. Archival tumor biopsy tissue and blood sample for pharmacogenomic analysis collected at baseline
- i. Quality-of-life questionnaire to be administered at baseline and at restaging

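### The MDASI is not clearly scheduled when treatment ends and Section 10.1 names no within-patient change, so a patient who stops before about week 18 may leave only a baseline score

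*Combined protocol and SAP*

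**What the plan says.** **Purpose.** Section 1.1.2 lists symptom assessment at baseline and at intervals as an exploratory objective. Section 3.4 goes further: the measures are to "capture the emergence or worsening of selected symptoms from baseline to study completion", with the further aim of "better capturing improvements in disease-related symptoms". It defines two component scores, the mean of the 13 symptom items and the mean of the 6 interference items.

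**Timing.** Sections 3.1 and 3.4 and footnote i of the study calendar (Section 3.5) agree. In the footnote's words: "Quality-of-life questionnaire to be administered at baseline and at restaging". Section 3.1 glosses restaging as response assessment. Restaging is every 6 cycles, plus or minus one, and a cycle is 21 days.

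**End of treatment.** The calendar row "Tumor measurements d" (the last letter is its footnote) is marked at Pre-Study and at Off Treatment. The questionnaire row is marked only at Pre-Study. Section 3.6.1 allows treatment to end at any time for toxicity, intercurrent illness or withdrawal, among other reasons. Follow-up after the last dose is a phone call about adverse events.

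**Analysis.** Section 10.1: "Symptom measurements will be summarized by mean and standard deviation for continuous measurements and by frequency distributions for categorical measurements". For the Notch readout the same paragraph says: "Modulation of the Notch pathway will be assessed by a paired t-test for a change in expression from baseline to post-drug administration".

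**The concern.** There are two gaps, and the first is the more urgent.

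- **Collection.** If no form is completed when a patient stops before the first restaging, any worsening that patient had is never recorded on the MDASI and cannot be recovered later. A patient who stops between later restagings has on-study scores but may have none at stopping.
- **Analysis.** The stated purpose is change within a patient. Means and SDs at each visit compare different groups of patients once anyone has left, and they do not give the precision of a change. This gap can be repaired later, because Section 3.4 says: "Questionnaires will be maintained in the research chart of each patient".

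What is at stake is the symptom objective only.

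**Working it through.** **Planned figures.** The documents state no sample size, expected score, SD, correlation or early-stopping rate for the MDASI, so there is no symptom figure to reproduce. The one figure the plan fixes is the timing of the first post-baseline form:

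- 6 cycles × 21 days = 126 days = week 18.
- 5 cycles = 105 days = week 15; 7 cycles = 147 days = week 21.

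Everything below uses assumed inputs and is illustrative. The only planned input is N = 17 (Section 10).

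**1. How many patients might leave only a baseline score.** Let d be the assumed share who stop before the first restaging with no exit form. The expected number is 17d, and the chance of at least one is 1 − (1 − d)^17.

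| d | Expected of 17 | Chance of at least one |
|---|---|---|
| 5% | 0.85 | 58% |
| 10% | 1.7 | 83% |
| 20% | 3.4 | 98% |
| 30% | 5.1 | 99.8% |

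**2. Worsening that is not captured.** Suppose 3 of 17 worsen by 2 points and stop before the first restaging, and the other 14 are unchanged. The mean change is 3 × 2/17 = +0.35. Restaging forms alone show 0.00. A form at stopping recovers +0.35. If half the worsening has eased by then it gives 3 × 1/17 = +0.18, and if all has eased, 0.00.

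**3. Means that move because of who remains.** Suppose 14 patients score 2, 3 score 6, nobody changes, and the 3 stop before the first restaging.

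- Baseline mean = (14 × 2 + 3 × 6)/17 = 46/17 = 2.71.
- Restaging mean = 2.00.
- Apparent change = −0.71, while every within-patient change is 0.

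**4. Precision.** Take 17 pairs and an assumed SD of √(1.6² + 1.0²) = 1.887 at each visit.

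- From separate means and SDs, a reader can form only the unpaired half-width: t(32) × 1.887 × √(2/17) = 2.037 × 0.647 = 1.32.
- Paired half-width: t(16) × 1.887 × √(2(1 − r)/17), where r is the correlation between visits and t(16) = 2.120.

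| r | 0 | 0.3 | 0.5 | 0.7 | 0.8 |
|---|---|---|---|---|---|
| Paired half-width | 1.37 | 1.15 | 0.97 | 0.75 | 0.61 |

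The ratio of paired to unpaired does not depend on the SD. At r = 0.5 it is (2.120/2.037) × √0.5 = 0.74. The paired interval is the narrower one once r exceeds 1 − (2.037/2.120)² = about 0.08.

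**The case against.** **An exit form may already be implied.** Tumor measurements are marked at Off Treatment and Section 3.1 equates restaging with response assessment, so site staff could reasonably give the form at that visit. Footnote d also requires radiologic documentation when a patient is removed for progression, so those patients should have a restaging. This stands, and it confines the gap to wording and mainly to patients who stop for other reasons. It does not close the gap, because no sentence requires the form at exit and two readers could act differently.

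**The blank Off Treatment cell.** A reader might infer from it that no exit form is collected. The documents do not support that. The questionnaire row also omits the restaging forms that footnote i requires, and the EKG and biopsy rows likewise leave out time points given in their footnotes. The blank cell settles nothing either way.

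**Descriptive summaries suit an exploratory objective.** They meet the wording of Section 1.1.2, nothing in Section 10.1 forbids change scores, and the contrast with the Notch analysis is weak because modulation is inherently a before-and-after question. All of this is fair. What remains is that Section 3.4 promises change from baseline and the analysis section does not carry it through.

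**An exit form has limits.** The MDASI looks back 24 hours, and Section 3.3 allows drug to be held for up to 3 weeks, so symptoms may have eased. Completion is supervised by clinic staff while some visits may be with a local physician, so a withdrawing patient may not complete it. Both points stand and are reasons to report the value as end-of-treatment with its date.

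**Conclusion.** A minor point that holds, mainly about scheduling and secondarily about Section 10.1. As written, a patient who stops before about week 18 (15 to 21) may leave only a baseline MDASI score, and the planned summary names no within-patient change.

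On the assumed scores above, the visit mean can shift by −0.71 with no patient changing, and the half-width of the interval for change is 0.97 paired against 1.32 unpaired at r = 0.5. At r = 0 pairing is slightly worse (1.37). The documents give no score distribution, correlation or early-stopping rate, so these figures show the mechanism and do not predict its size here.

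Two stronger conclusions are not supported. A reader might infer that change in patients with both forms is less biased than the planned means whatever the reason for drop-out. That depends on what drives drop-out, about which the documents are silent. Change computed only in those who stay can itself be biased when stopping is related to worsening. A reader might also infer that toxicity in early stoppers is lost. It is not: adverse events are graded by CTCAE, evaluated at Off Treatment and reported up to 30 days after the last dose. The primary response analysis is untouched.

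**What to change.** 1. **Calendar footnote i, with matching words in Sections 3.1 and 3.4.** State that the MDASI is completed at baseline, at each restaging and at the existing Off Treatment assessment, whatever the reason for stopping. Record the dates of the form and of the last dose, and report the score as an end-of-treatment value, separate from the restaging values.
2. **Section 10.1.** Beside the planned means, SDs and frequencies, add within-patient change from baseline in the two component scores at each restaging and, separately, at end of treatment. Give a 95% CI, the number of patients contributing, and the baseline scores of patients with no later form. Do not describe change in completers as free of drop-out bias.

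**Cost.** One extra form of 2-5 minutes at an assessment already in the calendar, and two or three sentences of text. The downside is that the exit score may understate worsening that has already eased, and some withdrawing patients will not complete it. For patients whose treatment has already ended, only the second change can still help, using the questionnaires kept in their charts.

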1. INTRODUCTION

1.1 STUDY OBJECTIVES

1.1.1 Primary Objective:

• Determine the response rate (CR+PR) of Nirogacestat in patients with desmoid tumors/aggressive fibromatosis

1.1.2 Exploratory Objectives:

- Assess symptoms at baseline and at intervals on study
- Perform genotyping for germline and somatic mutations in APC and CTNNB1 genes
- Correlate clinical response to therapy with genotyping data
- Assess modulation of the Notch pathway by evaluating notch response genes in tumor biopsies at baseline and post-drug administration

1.2 BACKGROUND AND RATIONALE:

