1.2.1 Desmoid Tumors

Desmoid tumors (also known as aggressive fibromatosis), are rare, locally invasive, slow-growing soft-tissue tumors. These tumors are considered benign; however, they are highly heterogeneous. The disease can be either asymptomatic requiring no intervention or be associated with severe loss of organ function and significant morbidity. Treatment options include wide surgical resection and radiotherapy, but not all tumors are amenable to resection and the post-surgical recurrence rate is high. Systemic chemotherapy may be indicated for inoperable or unresectable tumors, but watchful waiting may also be recommended as prolonged disease stabilization can occur [1-3].

Desmoid tumors frequently carry mutations in CTNNB1, the gene that encodes β -catenin, resulting in stabilization and nuclear accumulation of the protein [4-7]. β -catenin is an integral component of the Wnt/ β -catenin/Tcf signaling pathway, which is frequently dysregulated in cancer [8-10]. Patients with desmoid tumors carrying β -catenin mutations have a worse 5-year recurrence-free survival rate than patients with wild-type tumors [11, 12]. At least three different point mutations have been identified in exon 3 of CTNNB1 (T41A, S45F, and S45P), one of which (S45F) may be a predictor of tumor recurrence after resection. All three oncogenic mutations limit phosphorylation and consequently degradation of β -catenin, resulting in the protein being translocated to the nucleus to activate Wnt pathway target genes [11].

Patients with familial adenomatous polyposis (FAP) can also develop desmoid tumors as a result of somatic and germline mutations in the adenomatous polyposis coli (APC) tumor suppressor gene; these patients have an 800-fold increased risk of developing desmoids [1, 13-15]. APC protein is critical for preventing constitutive activation of Wnt signaling by regulating levels of β -catenin. In normal cells a multiprotein complex of APC, axin, casein kinase 1α (CK1 α) and glycogen synthase kinase (GSK3 β) regulates the phosphorylation of β -catenin, resulting in its

degradation [14, 16]. Mutations in the APC gene can generate altered or truncated protein which is unable to phosphorylate β -catenin. This results in increased in β -catenin that is subsequently translocated to the nucleus, resulting in activation of T cell transcription factor 4 (Tcf-4) and aberrant gene expression [9, 17] (Figure 1).

[figure not shown]

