Figure 1: Model of the Wnt/APC/beta-catenin pathway. Wnt protein binds to its receptor on the cell surface to increase accumulation of β -catenin, which is translocated to the nucleus, resulting in activation of Wnt pathway transcription factors (left panel). If an active APC complex forms, the complex can bind and phosphorylate β -catenin, leading to its subsequent ubiquitin-mediated degradation (right panel). If an active APC complex cannot form due to mutations in either APC or β -catenin itself, β -catenin is not degraded and remains constitutively active (Figure from [15]).

A limited number of clinical studies have been done due in part to the rarity of desmoid tumors; clinical activity has been reported in trials of targeted agents. Penel et al. reported one complete response and three partial confirmed responses (3% and 9%) in 40 patients with recurrent or established desmoid tumors in a Phase II clinical trial of the tyrosine kinase inhibitor imatinib [18]. Partial responses (6/13) and stable disease (8/13) were also reported in patients treated on an expanded access study with the multikinase inhibitor sorafenib [19].

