1.2.2 PF-03084014 (Nirogacestat)

Significant tumor shrinkage in patients with unresectable desmoid tumors was recently reported in a Phase I clinical trial of the small-molecule γ-secretase inhibitor PF-03084014 in patients with advanced solid tumors; four of nine evaluable patients with desmoid tumors experienced partial responses and the remaining five patients had some evidence of tumor shrinkage with prolonged disease stabilization [20, 21]. Gamma-secretase is required to activate intracellular

Notch signaling [22]. Notch pathway γ -secretase inhibitors have been postulated as a treatment for desmoid tumors as desmoid tumor-derived mesenchymal stromal cells express stem cell markers including BMI-1, a transcriptional repressor downstream of the Notch pathway [23]. A diagram outlining the complex potential interaction between components of the Notch and Wnt signaling pathways is presented in Figure 2 below:

[figure not shown]

Figure 2: Some of the embryonic signalling pathways that may interact to initiate and promote carcinogenesis: transforming growth factor (TGF)-β, Hedgehog (Hh), Notch, Wnt, and ErbB. From Takebe et al 2011 [24].

Preclinical Pharmacokinetics

Single dose pharmacokinetics of PF-03084014 following intravenous (IV) and oral administration was assessed in the toxicology species (rat and dog). PF-03084014 demonstrates moderate systemic clearance in rat and dog, with $T_{1/2}$ values of 11.7 and 12.4 hour, respectively. Systemic exposure increased with increasing dose in rats (2 to 50 mg/kg/day) and dogs (2, 10, and $50\rightarrow20$ mg/kg/day) from 3-month toxicological studies. Although the increase was greater than dose proportionality in the rats on both Day 1 and 90 and in the dogs on Day 1, the exposure increase was dose proportional in the dog on Day 91.

Volume of distribution at steady state values of PF-03084014 were greater than total body water in rats and dogs, suggesting that this compound readily distributes to tissues in these species. PF-03084014 showed high plasma protein binding with average unbound fraction (%) of 0.64, 1.95, 4.22, and 2.61 for mice, rats, dogs, and humans, respectively, at nominal concentrations of 490 ng/mL for mouse and 1,000 ng/mL for rat, dog and human determinations.

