with the longest diameter), be representative of all involved organs, but in addition should be those that lend themselves to reproducible repeated measurements. It may be the case that, on occasion, the largest lesion does not lend itself to reproducible measurement in which circumstance the next largest lesion which can be measured reproducibly should be selected. A sum of the diameters (longest for non-nodal lesions, short axis for nodal lesions) for all target lesions will be calculated and reported as the baseline sum diameters. If lymph nodes are to be included in the sum, then only the short axis is added into the sum. The baseline sum diameters will be used as reference to further characterize any objective tumor regression in the measurable dimension of the disease.

Non-target lesions. All other lesions (or sites of disease) including any measurable lesions over and above the 5 target lesions should be identified as **non-target lesions** and should also be recorded at baseline. Measurements of these lesions are not required, but the presence, absence, or in rare cases unequivocal progression of each should be noted throughout follow-up.

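### The genotype–response comparison in Section 10.1 uses only a yes/no response in at most 17 patients and leaves the measured percent change in tumor size unused

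*Combined protocol and SAP*

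**What the plan says.** Section 1.1.2 lists the exploratory objective: "Correlate clinical response to therapy with genotyping data". Section 10.1 turns it into one sentence: "The clinical response rate will be compared between the mutated and non-mutated subgroups". It names no test, error rate, effect measure or interval. It does not say whether a mutated tumor is one with a change in APC, in CTNNB1 or in either.

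Response is CR or PR, and PR is a fall of at least 30% in the sum of target diameters (Section 6.2.4.1). The sum itself is recorded. Section 6.2.2 says: "The baseline sum diameters will be used as reference to further characterize any objective tumor regression in the measurable dimension of the disease". Tumors are remeasured every 6 cycles, give or take one (Section 3.5, footnote d). I found no planned analysis of percent change, though the part of Section 5 between 5.1 and 5.2.2 was not available to me.

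On sample size, Section 10 says "then we plan to accrue a total of 17 patients". That number is set for the one-sample test of 10% v 35% response, not for any comparison between genotypes.

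**The concern.** Among few patients, a cut at -30% gives the same score to tumors that behaved differently. The protocol's own background shows this can matter. Section 1.2.2 reports four partial responses among nine evaluable Phase I desmoid patients, and "the remaining five patients had some evidence of tumor shrinkage with prolonged disease stabilization". A yes/no outcome cannot tell those five apart from each other or from a patient with no change.

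The groups may also be uneven. Section 1.2.1 says "Desmoid tumors frequently carry mutations in CTNNB1", which suggests a small CTNNB1 wild-type group but gives no figure.

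The grouping is open too. The Figure 1 legend treats the two genes as routes to the same end: "If an active APC complex cannot form due to mutations in either APC or" β-catenin itself, β-catenin stays active. If each gene were split separately, the CTNNB1 wild-type group could contain APC-mutated tumors with the same activation, which would blur the contrast.

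At stake is how much the trial can learn about genotype in a rare disease from measurements it already takes.

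**Working it through.** **The plan's own figure.** With n = 17 and rejection at 4 or more responses, the exact binomial gives P(X ≥ 4 | 0.10) = 0.083 and P(X ≥ 4 | 0.35) = 0.897. The stated 0.10 and 0.90 reproduce. No power is stated for the genotype comparison.

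**Inputs.** From the documents: at most 17 patients, and a response cut at -30%. Assumed because not stated: Fisher's exact test at two-sided 0.05; splits from 16:1 to 9:8; normally distributed percent change with equal SD.

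**Information kept by the cut.** Relative efficiency is φ(z_p)² / [p(1 − p)]. At p = 0.35, z = -0.385 and φ(z) = 0.370, so 0.370² / (0.35 × 0.65) = 0.137 / 0.2275 ≈ 0.60. Seventeen patients carry the information of about 17 × 0.60 ≈ 10.

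**A large difference.** Take mean changes of -35% and -5% with SD 20. The implied response rates are Φ((-30 + 35)/20) = Φ(0.25) = 0.60 and Φ((-30 + 5)/20) = Φ(-1.25) = 0.106. Fisher power is the sum of the two binomial probabilities over all tables with p ≤ 0.05. Wilcoxon power is simulated. Repeated simulations differ by up to about two points, and by symmetry Wilcoxon power is the same in both directions.

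| Split (mutated : non-mutated) | Fisher, mutated better | Fisher, non-mutated better | Exact Wilcoxon, either direction |
|---|---|---|---|
| 15:2 | 2% | 28% | 33–34% |
| 14:3 | 9% | 29% | 53–54% |
| 12:5 | 41% | 39% | 71–73% |

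Part of the gap is Fisher's conservatism rather than the cut. With 35% response in both groups, its true false-positive rate is about 0.8% at 15:2 and 1% at 14:3.

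**A modest difference.** Take 35% v 10% response, the design's p1 and p0. On the continuous scale this is d = z(0.35) − z(0.10) = -0.385 + 1.282 = 0.90 SD. With mutated tumors better, Fisher v Wilcoxon power is 0.1% v 13% at 15:2, 0.1% v 23% at 14:3, 5% v 33% at 12:5 and 9.5% v 38% at 9:8.

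**Limits set by the split alone.**
- At 16:1 the smallest two-sided Wilcoxon p is 2/17 = 0.118, so neither analysis can reach 0.05.
- At 15:2 with r responders, for r from 4 to 8, the smallest Fisher p is C(r,2)/C(17,2). That is 6/136 = 0.044 at r = 4, 10/136 = 0.074 at r = 5 and 28/136 = 0.206 at r = 8. From 5 to 12 responders it cannot fall below 0.074; at 4, the trial's own rejection threshold, it can reach 0.044.

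**The case against.** The aim is exploratory, claims no power and drives no clinical decision. The planned outcome matches both the stated objective and the primary endpoint. Nothing stops the investigators from showing percent change by genotype anyway. All of this stands, and it makes the point an improvement rather than the correction of an error.

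Four stronger readings are tempting, and the documents do not support them.

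- A reader might infer that the groups will be very unequal. The protocol gives no percentage, and Section 10.1 does not define the split.
- A reader might infer that the cut discards most of the information. By the usual efficiency formula it keeps about 60%.
- A reader might infer that the binary comparison has almost no power whatever the truth. With 80% v 10% response, Fisher has 52% power at 14:3 and 77% at 12:5. The direction also matters, and the protocol does not say which group should respond better. Section 1.2.1 reports worse recurrence-free survival with β-catenin mutations, so the reverse direction cannot be dismissed.
- A reader might infer that a real association would be reported as absent. No test or reporting rule is stated, so that is speculation.

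Two practical objections also stand. First restaging comes at about 6 × 21 = 126 days, or 18 weeks, whereas the Figure 3 legend says Phase I responses were measured after 6 to 9 months. Change at first restaging may therefore miss later shrinkage. And an exact percent change in 17 patients could help to identify someone in a data set that Section 5.4.2 requires to be untraceable.

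**Conclusion.** The point holds as a cheap gain in efficiency and clarity. Under the assumptions shown, the rank test on percent change has at least as much power as the response-rate comparison in every case tried. The gain is large when mutated tumors do better (9% to about 54% at 14:3) and small at 15:2 in the reverse direction (28% to about 34%).

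It does not rescue the aim. For a 25-point response gap with mutated tumors better, power stays at 38% or less at the splits tried, and at 16:1 significance at 0.05 is impossible. Small numbers remain the main limit.

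The result rests on assumed splits, normal outcomes with equal SD, a two-sided 0.05 level and a Fisher test that the plan does not name. Fewer than 17 patients may be evaluable under Section 6.2.1, which would lower every figure. The primary analysis is unaffected.

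**What to change.** In Section 10.1:

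- Add a comparison by genotype of best percent change from baseline in the sum of target diameters. Use an exact Wilcoxon or permutation test, with an effect estimate and confidence interval. Give change at first restaging as supportive.
- Keep response rate by genotype, with exact intervals.
- Classify each tumor once as CTNNB1-mutated, APC-mutated or neither, with a rule for a tumor carrying both, and name the two-group contrast to be tested.
- Label all of these results exploratory.

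In Section 5.4, state that percent change is carried into the data set before delinking, rounded or banded if needed to protect de-identification. Fix when the best value is taken: Section 5.4.1 allows delinking once a patient has responded, which could be before the largest shrinkage.

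The cost is about one paragraph in 10.1 and one variable in the delinked file. No new scans, visits or patients are needed. There are three small downsides. Percent change is missing for anyone without a restaging scan. Best percent change depends on time on study, so the first-restaging value is needed beside it. Rounding or banding gives up a little of the gained precision.
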